### **Loss of Efficacy (LoE)/Hypersensitivity reaction**

In case loss of efficacy is suspected by the investigator (ie, measured by low FVIII levels, poor recovery, and unexpected clinical symptoms of bleeding or no response to treatment of a bleed) or the participant presents symptoms of an hypersensitivity reaction, plasma samples will be tested for FVIII inhibitor and ADA, and positive screened samples will be further characterized for specificity of the antibody response against Jivi and/or against PEG. Samples that confirmed positive against Jivi will be further analyzed in a modified Nijmegen Bethesda assay for inhibitory activity against Jivi.

In addition to this, incremental recovery following administration of Jivi will be measured. Samples for Jivi trough and recovery levels following an injection of Jivi will be collected when loss of efficacy is suspected (See Section 8.1.2). In case of a slightly reduced recovery (compared to previous product or below 1.5 IU/dl per IU/kg), the recovery should be repeated locally after the next injection.

A clinical immune response manifested as symptoms of acute hypersensitivity and/or loss of drug effect has been observed primarily in children  $< 6$  years, within the first 4 exposure days, which was associated with anti-PEG antibodies. CC1

in such cases Jivi should be discontinued, participants should switch to a previously effective factor VIII product, and the recovery should be measured locally after injection of the previous FVIII which will be normal in these cases, ruling out an inhibitor.

#### **8.2.2 Physical Examinations**

- Physical examinations will be performed at Screening and End of Study/Early Termination Visit.

- A complete physical examination will include, at a minimum, assessments of the general appearance, dermatologic, head, eyes, ears, nose, mouth/throat/neck, thyroid, lymph nodes, cardiovascular, respiratory, gastrointestinal extremities, neurological and musculoskeletal and review of systems. Height and weight will also be measured and recorded.
- Body weight will be measured every 6 months (Visits 4, 5, and 6).
- Investigators should pay special attention to clinical signs related to previous serious illnesses. Any abnormal finding should be documented.

### **8.2.3 Vital Signs**

- Vital signs will be measured at Screening, Baseline, and End of Study/Early Termination Visit. In case of any in-hospital injection related AE, vital signs will be measured post-injection for participants.
- Heart rate, respiratory rate, and systolic and diastolic blood pressure will be assessed.
- Blood pressure and heart rate measurements should be preceded by at least 5 minutes of rest for the participant in a supine or seated position without distractions (e.g., television, cell phones).

### **8.2.4 Clinical Safety Laboratory Assessments**

- See Section 10.2 for the list of clinical laboratory tests to be performed and to the SoA for the timing and frequency.
- The investigator must review the laboratory report, document this review, and record any clinically relevant changes occurring during the study in the AE section of the CRF. The laboratory reports must be filed with the source documents. Clinically significant abnormal laboratory findings are those which are not associated with the underlying disease, unless judged by the investigator to be more severe than expected for the participant's condition.
- All laboratory tests with values considered clinically significantly abnormal during participation in the study should be repeated until the values return to normal or baseline or are no longer considered clinically significant by the investigator.
  - If such values do not return to normal/baseline within a period of time judged reasonable by the investigator, the etiology should be identified and the sponsor notified.
  - All protocol-required laboratory assessments, as defined in Section 10.2, must be conducted in accordance with the laboratory manual and the SoA.
  - If laboratory values from non-protocol specified laboratory assessments performed at the institution's local laboratory require a change in participant management or are considered clinically significant by the investigator (e.g., SAE or AE or dose modification), then the results must be recorded in the CRF.

## 8.3 Adverse Events and Serious Adverse Events

The definitions of an AE or SAE can be found in Section [10.3](#).

AE will be reported by the participant (or, when appropriate, by a caregiver, surrogate, or the participant's legally authorized representative or health care professional not involved in the study).

The investigator and any qualified designees are responsible for detecting, documenting, and recording events that meet the definition of an AE or SAE. They remain responsible for following up SAEs, or AEs considered related to the study intervention or study procedures, or those that caused the participant to discontinue the study. Events of Special Interest have to be followed up regardless of causality or relationship to study intervention (see Section [8.3.7](#)).

### 8.3.1 Time Period and Frequency for Collecting AE and SAE Information

All AEs and SAEs will be collected from the signing of the informed consent form (ICF) until the end of the final study visit at the time points specified in the SoA (Section [1.3](#)).

Medical occurrences that begin before obtaining informed consent but are diagnosed at screening or during the screening period (e.g., abnormal lab values) will be recorded on the Medical History/Current Medical Conditions section of the case report form (CRF), not the AE section.

All SAEs will be recorded and reported to the sponsor or designee immediately and under no circumstances should this exceed 24 hours, as indicated in Section [10.3](#). The investigator will submit any updated SAE data to the sponsor within 24 hours of it being available.

Investigators are not obligated to actively seek AE or SAE after conclusion of the study participation. However, if the investigator learns of any SAE, including a death, at any time after a participant has been discharged from the study, and he considers the event to be reasonably related to the study intervention or study participation, the investigator must promptly notify the sponsor.

### 8.3.2 Method of Detecting AEs and SAEs

The method of recording, evaluating, and assessing causality of AE and SAE and the procedures for completing and transmitting SAE reports are provided in Section [10.3](#).

Care will be taken not to introduce bias when detecting AEs and/or SAEs. Open-ended and non-leading verbal questioning of the participant is the preferred method to inquire about AE occurrences.

### 8.3.3 Follow-up of AEs and SAEs

After the initial AE/SAE report, the investigator is required to proactively follow each participant at subsequent visits/contacts. All SAEs and non-serious AEs of special interest (as defined in Section [8.3.7](#), will be followed until resolution, stabilization, the event is otherwise explained, or the participant is lost to follow-up (as defined in Section [7.3](#)). Further information on follow-up procedures is given in Section [10.3.3](#).

### 8.3.4 Regulatory Reporting Requirements for SAEs

- Prompt notification by the investigator to the sponsor of an SAE is essential so that legal obligations and ethical responsibilities towards the safety of participants and the safety of a study intervention under clinical investigation are met.
- The sponsor has a legal responsibility to notify both the local regulatory authority and other regulatory agencies about the safety of a study intervention under clinical investigation. The sponsor will comply with country-specific regulatory requirements relating to safety reporting to the regulatory authority, Institutional Review Boards (IRB)/Independent Ethics Committees (IEC), and investigators.
- Investigator safety reports must be prepared for suspected unexpected serious adverse reactions (SUSAR) according to local regulatory requirements and sponsor policy and forwarded to investigators as necessary.
- An investigator who receives an investigator safety report describing an SAE or other specific safety information (e.g., summary or listing of SAEs) from the sponsor will review and then file it along with the Investigator's Brochure and will notify the IRB/IEC, if appropriate according to local requirements.

### 8.3.5 Pregnancy

#### Contraception Guidance

- It has been shown that there is no target-related specific transport mechanism for Jivi into semen or from semen into the conceptus. Following administration to a male participant, Jivi would not be bioavailable via seminal delivery to the developing conceptus of an untreated partner. Therefore, no method of contraception is needed.

#### Collection of Pregnancy Information

- Bayer usually does not gather pregnancy information of drug exposure via father; however, if those cases are reported, details of all pregnancies in female partners of male participants will be collected after the start of study intervention and until one week period that is at least 5 terminal half-lives after the last dose.
- If a pregnancy is reported, the investigator should inform the sponsor of learning of the pregnancy.

### 8.3.6 Disease-Related Events and/or Disease-Related Outcomes Not Qualifying as AEs or SAEs

The following disease related outcome is common in participants with hemophilia A and can be serious/life threatening:

- Bleeding event

Any bleeding event, regardless if treated or not, occurring during the study will not be documented as an AE, because this is captured in the assessment of efficacy.

Because these events are typically associated with the disease under study, they will not be reported according to the standard process for expedited reporting of AEs. These events will be recorded in the EPD.

*NOTE: However, if the bleed fulfills the criterion for an SAE (e.g. results in hospitalization), then the event should be recorded and reported as an SAE (see Section 10.3.2).*

### **8.3.7 Events of Special Interest**

Hypersensitivity reactions are a known and listed adverse drug reactions for FVIII products and have been reported with use of Jivi. Loss of efficacy of the drug product has also been reported in children < 6 years of age and may be associated with the development of antibodies to PEG. All such reported events occurred early in treatment, within the first 4 ED. Both of these events are defined in this study as adverse events of special interest and must be reported as adverse events.

In the event of such a hypersensitivity reaction or reported loss of efficacy of the treatment product, antibody and inhibitor testing will be obtained. Loss of efficacy needs to be documented by pre and post factor VIII levels around an injection of the Jivi, using appropriate laboratory measures, and be confirmed in the central laboratory.

CCI

### **8.4 Treatment of Overdose**

Sponsor does not recommend specific treatment for an overdose.

### **8.5 Pharmacokinetics**

PK parameters are not evaluated in this study.

### **8.6 Pharmacodynamics**

Pharmacodynamic parameters are not evaluated in this study.

### **8.7 Genetics**

Genetics parameters are not evaluated in this study.

### **8.8 Biomarkers**

Biomarkers for renal safety will be evaluated in the study (see Section 10.2 Appendix 2).

## 8.9 Other investigations

CCI

CCI

CCI

## 8.10 Health Economics OR Medical Resource Utilization and Health Economics

Health Economics/Medical Resource Utilization and Health Economics parameters are not evaluated in this study.

## 9. Statistical Considerations

### 9.1 Statistical Hypotheses

The study is not designed to test any predefined hypothesis. All analyses will be descriptive or exploratory.

### 9.2 Sample Size Determination

Descriptive statistics will be used. The sample size is defined by the Note for guidance on the clinical investigation of recombinant FVIII products in order to fulfill post-marketing requirements. During the clinical development program, a total of 232 participants were included in the Phase 1 and 2/3 clinical development program. Among these participants, 168 participants achieved >100 ED, and additional 17 participants achieved 50-100 ED. It is considered, that at least additional 25 participants would support the assessment of general safety and efficacy as required by guidelines EMA/CHMP/BPWP/144533/2009 rev.2 ([EMA 2017](#)).

A pooled analysis will be performed for all patients included in the Phase III and IV studies. The following trials will be included in the pooled analysis:

Study	Total number of participants included
PROTECT VIII	134
PROTECT Kids	73
Planned Phase IV study	≥25
Expected total	≥232

Assessment of safety will be done for the safety population including all participants with at least 1 injection of Jivi. Assessment of efficacy will be performed for the ITT population including participants with diary/injection data available.

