### Overall Design:

The study will be a multicenter, single group, uncontrolled open-label trial. Severe hemophilia A patients, age  $\geq 18$  years, will be enrolled and treated with prophylaxis treatment and for breakthrough bleeds for at least 100 exposure days (ED), which may require 1-2 years depending on the prophylaxis regimen. Assessment of immunogenicity/safety will be performed at pre-defined ED as required by the EMA FVIII Guideline. The recommended starting dose is every 5 days treatment (45 IU/kg). Response to treatment will be assessed at the next visit after 10-15 ED, scheduled for inhibitor assessment as per Guideline. Participants may be assigned to different dosing regimens (every 7 days or 2x/week) or continue with every 5 days regimen, according to individual bleeding tendency and needs at investigator's discretion. Clinical general safety, efficacy, and immunogenicity will be assessed at baseline, 10-15 ED, 50-75 ED and after approximately 100 ED.

This study will address regulatory requirements of assessment of safety in a total of 200 participants with 100 ED including pre-licensure participants of the development program from the studies #13024 Protect VIII and #15912 Protect Kids. This study will include at least 25 participants for fulfillment of the requirement and provide a pooled analysis of all clinical studies (phase III/IV) including at least 200 participants observed for at least 100 ED.

The study will assess the important identified risks of development of Factor VIII (FVIII) inhibitors, hypersensitivity, and potential lack of drug effect associated with anti-polyethylene glycol (PEG) antibodies during the first exposures to Jivi and long-term treatment up to 100

ED. An optional interim analysis will be performed, if needed for regulatory submission or publication purposes, after all participants have been treated for 6 months.

**Intervention Model:** Single Group

**Primary Purpose:** Treatment

**Number of Arms:** Single arm

**Masking:** No masking

**Number of Participants:** Approximately 25-30 participants will be assigned to the study intervention. At least 25 participants are expected to complete the study. The study is completed when 25 participants have reached 100 ED.

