## 4.2 Scientific Rationale for Study Design

The study is designed according the requirements defined in the “Guideline on the clinical investigation of recombinant and human plasma-derived factor VIII products” EMA/CHMP/BPWP/144533/2009 rev.2 ([EMA 2017](#)). The total sample size was chosen in order to fulfil Guideline requirements of 200 participants observed for at least 100 ED.

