## 4.4 End of Study Definition

A participant is considered to have completed the study if he has completed all phases of the study including the last visit or the last scheduled procedure shown in the Schedule of Activities. If more than 25 participants are included, all participants will be treated for at least 6 months, but not all participants may reach 100 ED at the end of the study.

The end of the clinical trial in each participating country is achieved with LPLV in the country. The end of the overall study is defined as LPLV and the last data from the last visit are received.

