## **1. Introduction**

Recombinant coagulation FVIII (rFVIII) is a replacement therapy in patients with Hemophilia A. Jivi (BAY 94-9027) has received marketing authorization amongst others from Food and Drug Administration (FDA), European Medicines Agency (EMA), Japanese Pharmaceuticals and Medical Devices Agency (PMDA), and Health Canada. The approved indication is: Treatment and prophylaxis of bleeding (including perioperative management) in previously treated patients (PTPs)  $\geq$  12 years of age with hemophilia A (congenital FVIII deficiency).

Regulatory requirements necessitate to assess the safety of Jivi in a total of 200 participants with 100 exposure days (ED) including pre-licensure participants of the development program from the studies 13024 (PROTECT VIII) and 15912 (PROTECT Kids). This study will include at least 25 participants for fulfillment of the requirements and provide a pooled analysis of all clinical studies (phase III/IV).

The purpose of this statistical analysis plan (SAP) is to describe the procedures and statistical methods to be used in analyzing and reporting results for the assessment of safety and efficacy of Jivi in Study 19764 and the integrated analysis of this study together with studies 13024 Part A (incl. extension) and 15912 (incl. extension).

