## **2. Study Objectives**

The objective of the study is to confirm general safety and clinical efficacy with specific focus on immunogenicity and inhibitor documentation in a routine clinical use of the product in at least additional 25 participants during 100 ED in order to fully comply with Guideline requirements of 200 participants observed for at least 100 ED including participants from pre-authorization studies.

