**Table 3-1: Recommended dose regimen**

Procedure	Duration	Dose regimen	Route of administration
Screening	> 2 weeks, ≤ 8 weeks	Continuation of previous treatment	
	Time to reach 10- 15 ED (~ 8 to 10 weeks)	Recommended starting dose 45 IU/kg every 5 days. Dose regimen can be adjusted any time in case of bleeds	IV injection
	Time to reach 100 ED	
0 bleeds during the first 8-10 weeks:
 
1 clinically relevant bleed during the first 8-10 weeks:
 
≥ 2 clinically relevant bleeds during the first 8-10 weeks:
	
Recommended dose regimen: 60 IU/kg every 7 days
 
Continue every 5 days at dose of 60 IU/kg
 
Or at investigator's judgement: Switch to 40 IU/kg 2x/week

Treatment Phase			IV injection

ED = exposure day, IV = intravenous

Clinically relevant: joint or muscle bleed that needs treatment

The total treatment duration is the time to reach 100 ED of Jivi. The total duration of study participation for each participant may require up to 2 years depending on the selected prophylactic regimen. When 25 participants have reached 100 ED, the study will be completed. Remaining participants may prematurely discontinue with reason 'Study terminated by sponsor' when a treatment duration of at least 6 months is reached.

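### Protocol 9.2 gives 168 + 25 = 193 pooled participants with 100 exposure days when the study closes, not the 200 or more on which the sample size rests

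*Protocol*

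**What the plan says.** Protocol 4.2 gives the basis for the size: "The total sample size was chosen in order to fulfil Guideline requirements of 200 participants observed for at least 100 ED". Protocol 1.1 and 4.1 commit the study to "provide a pooled analysis of all clinical studies (phase III/IV) including at least 200 participants observed for at least 100 ED". SAP 2 sets the objective in the same terms: "in order to fully comply with Guideline requirements of 200 participants observed for at least 100 ED including participants from pre-authorization studies". Protocol 9.1 states no hypothesis, so there is no power calculation behind the number.

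Protocol 9.2 describes a Phase 1 and 2/3 programme of 232 participants and reports: "Among these participants, 168 participants achieved >100 ED, and additional 17 participants achieved 50-100 ED". Its table then lists the pool as PROTECT VIII 134, PROTECT Kids 73 and this study at least 25, for an expected total of at least 232.

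The closing rule is in the synopsis, "The study is completed when 25 participants have reached 100 ED", and in SAP 3, "When 25 participants have reached 100 ED, the study will be completed". About 25 to 30 participants are to be treated. For those beyond the first 25, Protocol 4.4 guarantees 6 months of treatment, "but not all participants may reach 100 ED at the end of the study".

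**The concern.** The study exists to bring a regulatory count up to 200, and that count is the only numerical basis offered for recruiting 25 people. The reader expects 9.2 to show that the earlier count plus 25 reaches 200. It does not. The number it gives for earlier participants with enough exposure is too small. The total it does display counts everyone included, whatever their exposure, and could be mistaken for evidence that the target is exceeded.

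The closing rule refers only to the 25 new completers and not to the pooled count. If there is a real shortfall, it could come to light only after the study has closed, when the stated objective can no longer be met from this study.

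**Working it through.** **Inputs**

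| Quantity | Value | Source |
|---|---|---|
| Target, pooled participants with at least 100 ED | 200 | Protocol 1.1, 4.1, 4.2; SAP 2 |
| Earlier participants with more than 100 ED | 168 | Protocol 9.2 |
| Earlier participants with 50-100 ED | 17 | Protocol 9.2 |
| Phase 1 and 2/3 programme | 232 | Protocol 9.2 |
| Earlier studies in the pool | 134 and 73 | Protocol 9.2 table |
| New completers at closure | 25 | Protocol 1.1; SAP 3 |
| Top of planned enrolment | 30 | Protocol 1.1 |

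**Step 1. Reproduce the plan's own total.** 134 + 73 + 25 = 232. The table adds up, but it counts participants included, not participants with at least 100 ED.

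**Step 2. Count those with enough exposure.**
- At the closing rule: 168 + 25 = 193; 200 − 193 = 7 short.
- If all 30 finish: 168 + 30 = 198; 200 − 198 = 2 short. The target is a minimum, so being close to it does not meet it.
- If the 168 stands, the completers needed are 200 − 168 = 32, above the planned 25 to 30.

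**Step 3. What the two earlier studies must supply.** Together they hold 134 + 73 = 207 participants.
- With 25 completers: 200 − 25 = 175, which is 175/207 = 84.5% of them.
- With 30 completers: 200 − 30 = 170.
- Even if all 168 belong to these two studies, 175 − 168 = 7 more are needed. If they come from the 17 at 50-100 ED, that is 7/17 = 41% of that group (with 30 completers, 2/17 = 12%).

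**Step 4. Range with 25 completers, under stated assumptions.**
- All 168 are in the pool and between 0 and 17 of the 17 have since reached 100 ED: 193 to 168 + 17 + 25 = 210. This is not a strict upper limit, because 232 − 168 − 17 = 47 programme participants fall in neither category and some may have accrued exposure in the extensions.
- Lower extreme: assume the 207 are all among the 232 and nobody is counted twice. Then 232 − 207 = 25 programme participants lie outside the two studies. If all 25 were among the 168 and nobody has moved up, the pool supplies 168 − 25 = 143, and 143 + 25 = 168. Nothing in the documents says that this is so; it marks how far the missing breakdown could matter.

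**The case against.** The best counter-argument is that this is a missing reconciliation rather than a demonstrated shortfall. No sum printed in 9.2 is wrong, and the 168 may be an old snapshot. The original protocol dates from March 2019 and the amendment table lists no change to 9.2. The SAP cites a 13024 protocol and earlier-study SAPs from later in 2019, and the pool includes both extensions. Exposure may therefore have kept accruing after the 168 was counted. A count of more than 100 ED also leaves out anyone at exactly 100. All of this is fair, and it is why the conclusion stops short of saying that the target will be missed. But the dates are only suggestive, and no passage says that any further participant reached 100 ED.

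It can also be said that the pooled count will be reported anyway, since Protocol 9.4.2 plans integrated exposure tables and SAP 6.1 has a category for 100 ED or more. That is true, but those tables come at analysis, after the closing rule has been applied.

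Protocol 9.2 also says that at least 25 more would support the assessment of safety and efficacy that the guideline calls for. That gives a purpose but no arithmetic, so 200 remains the only number from which 25 could be derived.

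Two cautions stand. The ends of the range in Step 4 rest on assumptions and should not be read as likely values. And rewording the target downwards would make the documents accurate but would not deliver the 200.

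**Conclusion.** The concern holds. On the documents' own figures the pooled count at closure is 193, 7 below the stated minimum of 200, and 198 if 30 participants complete. These sums assume that all 168 earlier participants belong to the two pooled studies and that none has been added since. The first assumption may make the total too high; the second, together with the exclusion of those at exactly 100 ED, may make it too low. Whether 200 is reached in fact cannot be told from the protocol or SAP. What can be said is that 9.2 does not support the claim for which the sample size was chosen, and that the study can close without anyone having shown that the claim is met. This should be corrected, because it affects both the stated objective and the only numerical basis for the sample size.

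**What to change.** 1. In Protocol 9.2, replace the 168 with a dated count of participants with 100 ED or more (not more than 100) from 13024 Part A and 15912, including their extensions.
2. Add a column for 100 ED or more to the 9.2 table, beside the headcount, and show the sum: that count + 25, compared with 200. The test is whether the count is at least 175.
3. If the count is below 175, restate the 200 and the full-compliance wording at the number the design delivers, in Protocol 1.1, 2.1, 3, 4.1 and 4.2 and SAP 1 and 2. If the sponsor prefers to keep 200, the closing rule would instead have to be tied to the pooled count, with 200 minus that count as the number of completers needed.

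Steps 1 and 2 cost one count and one table column. They need no new data: SAP 7 describes the 13024 and 15912 results as already available, and SAP 6.1 already defines the exposure category. Step 3 costs wording only if the target is restated; keeping 200 would mean more completers and longer follow-up.
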